10.3.4 Other Safety Measures

10.3.4.1 *Physical Examination*

A complete physical examination including assessments of general appearance, skin, head (eyes, ears, nose, and throat), lungs, heart, abdomen, back, lymph nodes, extremities, and neurological system will be completed at screening and at end of treatment. Directed physical examinations will be completed at additional time points as specified in the schedule of events. The results of all time points will be displayed in a listing.

10.3.4.2 *Electrocardiogram*

Please refer to [Appendix A](#), [Appendix B](#) and [Appendix C](#) for the schedule of events.

ECG results including: Heart Rate, QT Interval, QTc Interval and method, and classification of Within Normal Limits, Abnormal Not Clinically Significant, and Abnormal Clinically Significant with a description for abnormal findings will be presented in data listings.

QTcB based on Bazetts' formula or QTcF based on Fredericia's formula will be listed for all subjects under the method used by the local laboratory. The denominator for the summaries will be the number of subjects who had non-missing values at each visit time point. Only scheduled visits will be included in summary tables. All visits will be included in listings.

Number and percentage of subjects in the following categories will be tabulated by cohort and overall for QTcF and QTcB:

- > 450 ms;
- > 480 ms;
- > 500 ms;
- change from baseline > 30 ms;
- change from baseline > 60 ms;
- > 500 ms and/or change from baseline > 60 ms;

where they can be calculated using the following:

- Bazett's Formula: QTcB = QT / square-root (RR Interval);
- Fredericia's Formula: QTcF = QT / cube-root (RR Interval);
- RR Interval = 60 / Heart Rate.

The categories used in the tabulation are not mutually exclusive. Additionally, for the tabulations, where the local laboratory did not provide both a QTcB and a QTcF value, the values that were missing will be derived using the above formulas.

Shift from baseline to worst post-baseline ECG results will be presented by cohort and overall.

10.3.4.3 *B-Symptoms*

B-symptoms are defined as at least one of the following:

- unexplained fevers greater than 38°C
- drenching night sweats
- weight loss greater than 10% of normal body weight over a period of 6 months or less.

B-symptoms will be documented at screening, prior to every cycle and at end of treatment. All results will be displayed in a data listing.

10.4 Extent of Exposure

Debio 1562 will be given intravenously:

- On day 1 of each 21-day cycle for subjects assigned to a Debio 1562 Q3W dosing schedule cohort. Planned Debio 1562 dose for the Q3W dosing schedule is 0.7 mg/kg;
- On day 1, day 8 and day 15 of each 21-day cycle for subjects assigned to the Debio 1562 QW dosing schedule cohort. Planned Debio 1562 dose for the QW dosing schedule is 0.4 mg/kg, 0.2 mg/kg and 0.2 mg/kg at day 1, day 8 and day 15 of each cycle.

Rituximab will be given intravenously on day 1 of each 21-day cycle after the infusion of Debio 1562. Planned dose for rituximab is 375 mg/m².

For Debio 1562, the total dose of drug will be calculated based on each subject's body weight. The weight used for calculation should be obtained prior to first treatment and thereafter should only be modified for relevant ($\geq 10\%$) changes in baseline body weight (not influenced by weight gain or loss attributed to fluid retention).

The exposure to Debio 1562 and rituximab will be summarized by cohort and overall, with summary statistics including mean, standard deviation, median, minimum, and maximum on:

- **Number of treatment cycles**, defined as the number of cycles in the eCRF where non-zero dose of Debio 1562 was infused;
- **Treatment duration**, expressed in weeks. It is calculated as:
$$\text{Ceiling} ((\text{date of last cycle day 1} - \text{date of first dose} + 21) / 7);$$
- **Total cumulative dose**, expressed in mg. It is calculated as the sum of the actual dose administered in all cycles while the subject is on study drug;
- **Actual dose level**:
 - o Debio 1562 actual dose level, expressed in mg/(kg*cycle). It is calculated as:
$$\text{Total cumulative dose of Debio 1562 (mg)} / (\text{average pre-dose weight (kg)} * \text{number of cycles})$$
 - o Rituximab actual dose level, expressed in mg/(m²*cycle). It is calculated as:
$$\text{Total cumulative dose of rituximab (mg)} / (\text{average pre-dose Body Surface Area (BSA) (m}^2\text{)} * \text{number of cycles})$$

Relative dose intensity per week (over the treatment duration)

- **Relative dose intensity per week**, expressed in %. It is calculated as: $\text{Actual dose intensity} / \text{planned dose intensity} * 100$
- **Actual dose intensity**, expressed in mg/week. It is calculated as:
$$\text{Total cumulative dose (mg)} / \text{duration of dosing (weeks)}.$$
- **Planned dose intensity**, expressed in mg/week. It is calculated as
$$\text{Total planned cumulative dose in a cycle (mg/kg or mg/m}^2\text{)} * \text{pre-dose weight (kg) or BSA (m}^2\text{)} / 3 (\text{weeks})$$

The pre-dose weight used for this calculation should be obtained prior to first treatment, i.e. at Cycle 1 Day 1, and thereafter should only be modified for significant ($\geq 10\%$) changes in body weight.

Relative dose intensity (Listing)

- **Relative dose intensity**, expressed in %. It is calculated as: actual cumulative dose received / planned cumulative dose during the same number of cycles * 100, where:
- **The number of cycles** for this calculation will be taken as the number of initiated cycles up
- to Cycle 6 included, or until PD, or until decision to end the treatment, whichever comes first.
- **The actual cumulative dose received** will be calculated as the sum of doses that have been administered during the above-defined number of cycles.
- **The planned cumulative dose** will be calculated as the planned per protocol dose (for Debio 1562: 0.8 mg/kg for Cohort B, 0.7 mg/kg for all other cohorts; for rituximab: 375 mg/m²) multiplied by the number of cycles initiated (up to Cycle 6 or until PD, or until decision to end the treatment, whichever comes first).

The number and percentage of subjects who had interrupted, missed, delayed, or decreased dosing, and the reason(s) will be summarized for Debio 1562 and rituximab. For each modification action, each distinct reason will be reported in each specific category.

Supportive by-subject listings of Debio 1562 and rituximab infusions will be presented.

Infusion rate will be obtained from the relevant data in the EDC but also calculated as (mg in infusion)/(time of treatment end – time of treatment start). Both will be presented in listings.

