#### 5.9.2.1 Adverse Events Requiring Permanent Study Treatment Discontinuation

Both Debio 1562 and rituximab should be permanently discontinued in the case of the following treatment-related events:

- $\geq$  Grade 3 cardiac event
- $\geq$  Grade 3 cutaneous reactions related to rituximab treatment
- Other non-hematologic events of Grade 4 severity
- Grade 4 thrombocytopenia lasting  $>7$  days
- $\geq$  Grade 3 neuropathy
- Dose delay  $> 21$  days due to unmet retreatment criteria

Rituximab should be permanently discontinued in patients experiencing the AEs listed in [Table 6](#).

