#### 5.9.2.2 Adverse Events Requiring Dose Reduction

Rituximab dose reductions are not allowed. If patients do not tolerate treatment with rituximab, they may continue on Debio 1562 alone.

For **Cohort A**, dose reduction of Debio 1562 will occur as follows:

- 0.7 mg/kg → 0.4 mg/kg

For **Cohort B**, dose reduction of Debio 1562 will occur as follows:

- 0.4 mg/kg → 0.2 mg/kg
- 0.2 mg/kg → 0.1 mg/kg

Dose of Debio 1562 should be reduced in patients experiencing the AEs below:

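### SAP 10.4 gives no rituximab cycle count, so the rituximab actual dose level appears to be averaged over Debio 1562 cycles and cannot separate early stopping from lower dosing

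*SAP*

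**What the plan says.** SAP 10.4 (Extent of Exposure) has one list of summary measures for both drugs. The list contains a single cycle count, the number of treatment cycles, "defined as the number of cycles in the eCRF where non-zero dose of Debio 1562 was infused". Further down it introduces the rituximab measure: "Rituximab actual dose level, expressed in mg/(m²*cycle). It is calculated as" total rituximab in mg divided by the product of average pre-dose body surface area and number of cycles. The Debio 1562 measure has the same form, with body weight in place of surface area. No count of rituximab cycles is defined or listed for reporting.

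The same section states the planned dose: "Planned dose for rituximab is 375 mg/m²", on Day 1 of each 21-day cycle.

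The protocol provides for cycles with Debio 1562 and no rituximab. Section 5.9.2.2 says: "Rituximab dose reductions are not allowed. If patients do not tolerate treatment with rituximab, they may continue on Debio 1562 alone". Section 5.9.2.1 adds that "Rituximab should be permanently discontinued in patients experiencing the AEs listed in" Table 6. Section 4.1.1, under study treatment duration, repeats that single-agent Debio 1562 may continue after intolerance to the combination.

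**The concern.** For Debio 1562, the cycle count and the dose being averaged refer to the same drug. For rituximab they do not, if the count is the one defined in the list. A patient who stops rituximab and stays on Debio 1562 keeps adding cycles to the denominator and nothing to the numerator, so the rituximab figure falls with every further Debio 1562 cycle.

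The mismatch works mainly in one direction. Section 5.9.2.2 of the protocol stops both drugs when Debio 1562 cannot be tolerated, so rituximab-only continuation is largely ruled out.

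What is at stake is the reading of one exposure table. A measure called an actual dose level invites the reader to take it as the size of dose given. As written, it mixes dose size with time on rituximab, and the table contains no rituximab cycle count that would let a reader separate the two.

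**Working it through.** The plan states no figure to reproduce here, so the check applies the SAP formula to simple cases.

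**Inputs**
- Planned rituximab dose: 375 mg/m² per cycle (SAP 10.4).
- Planned treatment: six cycles, longer by exception (Protocol 4.1.1).
- Denominator count: cycles with a non-zero Debio 1562 dose (SAP 10.4), read as the number of cycles in the rituximab formula.
- Assumptions: body surface area (BSA) is constant within a patient, and each rituximab infusion is given in full.

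**Formula.** With k full rituximab doses over n Debio 1562 cycles:

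total rituximab (mg) = k × 375 × BSA

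actual dose level = (k × 375 × BSA) / (BSA × n) = 375 × k/n

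BSA cancels, so patient size does not matter. With k = n = 6 the formula returns the planned 375.

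**Six Debio 1562 cycles**

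| Full rituximab doses (k) | SAP formula, mg/m² per cycle | Divided by rituximab cycles |
|---|---|---|
| 1 | 62.5 | 375 |
| 2 | 125 | 375 |
| 3 | 187.5 | 375 |
| 4 | 250 | 375 |
| 5 | 312.5 | 375 |
| 6 | 375 | 375 |

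If treatment is extended to 10 Debio 1562 cycles after 3 rituximab doses, the figure is 375 × 3/10 = 112.5.

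**Effect on a cohort mean.** The documents do not say how many patients would stop rituximab alone. For illustration, assume 30 patients with six Debio 1562 cycles each, of whom m stop rituximab after three doses:
- m = 1: (29 × 375 + 1 × 187.5)/30 = 368.75
- m = 3: (27 × 375 + 3 × 187.5)/30 = 356.25
- m = 6: (24 × 375 + 6 × 187.5)/30 = 337.5

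The reported minimum would be 187.5 in each case.

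**Does the other cycle definition help?** For the relative dose intensity listing, SAP 10.4 counts initiated cycles up to Cycle 6, progression or the decision to end treatment. That definition is confined to the listing. It would not drop Debio-only cycles either: 3 rituximab doses in 6 initiated cycles give (3 × 375)/(6 × 375) = 50%, the same dilution as 187.5/375. For a relative dose intensity, that is the intended behaviour.

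**The case against.** Several counter-arguments carry weight.

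- **The denominator is inferred.** The formula says number of cycles; the defined term is number of treatment cycles, and the formula does not point to it. A per-drug reading is possible. This stands as a caution on wording. But no per-drug count is defined, and the only other definition dilutes in the same way, so the text needs completing under any reading.
- **A per-cycle average is a legitimate quantity.** The unit is per cycle, not per infusion. For a patient on treatment for six cycles with rituximab in two, 125 is a correct average over treatment cycles. A reader might infer an arithmetic error, and the documents do not support that. The problem is one of definition and labelling.
- **Omitted doses lower the Debio 1562 figure too.** In Cohort B, a Day 8 or Day 15 dose that fails the retreatment criteria is skipped (Protocol 5.9.1), yet the cycle counts. One skipped 0.2 mg/kg dose gives 0.8 − 0.2 = 0.6 mg/kg for that cycle. The measure therefore does not isolate dose size for Debio 1562 either. For rituximab, however, whole cycles without the drug enter the denominator.
- **Other outputs show the stop.** SAP 10.1.2 tabulates rituximab discontinuation separately, with reasons. SAP 10.4 summarises missed and decreased dosing by drug and lists every infusion. This largely stands: a reader who combines the outputs can work out what happened.
- **The corrected measure will vary little.** Because "Rituximab dose reductions are not allowed", dividing by rituximab cycles should give values close to 375 for nearly everyone. That is fair, and it makes the added rituximab cycle count the more informative part of the change.

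**Conclusion.** The point holds as a minor matter of definition. SAP 10.4 supplies only a Debio 1562 cycle count, and the rituximab actual dose level appears to use it. For patients who stop rituximab and continue Debio 1562 alone, the result is 375 × k/n and cannot separate early discontinuation from lower dosing. The size for an individual can be large (250 for 4 of 6 doses, 125 for 2 of 6). The effect on a cohort summary depends on how many such patients there are, which the documents do not give.

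A reader might infer that the table would report a rituximab dose reduction of the kind the protocol prohibits. The documents do not support that: no output labels the figure a reduction, decreased dosing is a separate category, and the prohibition concerns the dose given, not an average across cycles.

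The conclusion assumes constant body surface area, full infusions, and the cycle count being the one defined in the list. One descriptive exposure summary is affected. No response or survival result, futility rule or safety rule uses it.

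**What to change.** In SAP 10.4:

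1. Define the number of cycles for each drug. For rituximab, count cycles in which a non-zero rituximab dose was infused.
2. State that the rituximab actual dose level divides by the rituximab count.
3. Report the number of rituximab cycles beside it, so that early stopping appears as duration.
4. Leave the combined effect of dose size and early stopping to relative dose intensity, which the section already provides.

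The cost is a line or two of SAP text and a small programming change. No new data are needed, since rituximab infusions are already recorded and listed by subject. The change concerns reporting only and touches no dose or treatment rule.

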#### **5.7.2. Debio 1562 Preparation**

The total dose of Debio 1562 will be calculated based on each patient's body weight. The weight used for calculation should be obtained prior to first treatment and thereafter should only be modified for significant ( $\geq 10\%$ ) changes in body weight (not influenced by weight gain or loss attributed to fluid retention). Further information about dosing requirements is outlined in the Pharmacy Manual.

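### SAP 10.4 does not apply one dosing-weight convention to its exposure metrics, so some correctly dosed patients will show a dose that differs from plan

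*SAP*

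**What the plan says.** **Dosing rule.** Protocol 5.7.2 states: "The weight used for calculation should be obtained prior to first treatment and thereafter should only be modified for significant" changes of 10% or more. Both that section and the opening of SAP 10.4 add that the change must be "not influenced by weight gain or loss attributed to fluid retention". For rituximab, Protocol 5.7.3 and Appendix J also fix the weight behind the BSA, subject to a 10% rule.

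**Exposure metrics in SAP 10.4.**

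- *Actual dose level* is total cumulative dose over "average pre-dose weight (kg") times number of cycles. Rituximab uses average BSA in the same way. Neither the 10% rule nor the fluid exception is mentioned.
- *Planned dose intensity* has its own rule: "The pre-dose weight used for this calculation should be obtained prior to first treatment, i.e. at Cycle 1 Day 1". It then allows modification for changes of 10% or more, without the fluid exception.
- *Relative dose intensity (listing)* takes the planned dose as "0.8 mg/kg for Cohort B, 0.7 mg/kg for all other cohorts" (375 mg/m² for rituximab), multiplied by cycles initiated. It names no weight or BSA to convert this to mg.

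**The concern.** A dose-delivery metric should return the planned value when the patient was dosed exactly as the protocol requires. That happens only if the weight in the metric is the weight that set the dose. Here the section states the dosing rule once and then departs from it in different ways. A patient who gains fluid weight and stays on the same mg dose has followed the protocol, yet planned dose intensity can treat that patient as under-dosed. For actual dose level, ordinary weight drift below 10% could appear as a dose deviation. Two programmers working from this text could also produce different tables. At stake is the accuracy of individual exposure figures in the report.

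**Working it through.** **Inputs**

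- Numerator (SAP 10.4): the "sum of the actual dose administered in all cycles while the subject is on study drug".
- Number of cycles (SAP 10.4): "the number of cycles in the eCRF where non-zero dose of Debio 1562 was infused". Six is the planned maximum (SAP 4.1.2).
- Planned dose: "Planned Debio 1562 dose for the Q3W dosing schedule is 0.7 mg/kg" (SAP 10.4). Cohort B: 0.4 + 0.2 + 0.2 = 0.8 mg/kg per cycle.
- Weight is re-measured on Day 1 of every cycle, and also on Days 8 and 15 in Cohort B (schedules of events, Appendices B and C).
- Weight paths: assumptions, because the documents give no weight-change data. W is the Cycle 1 Day 1 weight, taken as the dosing weight.

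**Check at constant weight**

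- Actual dose level: (6 × 0.7W) / (W × 6) = 0.700 mg/kg per cycle. For Cohort B, 0.800. Both match plan.
- Weekly dose intensity: actual 4.2W/18 weeks = 0.233W; planned 0.7W/3 = 0.233W. Relative dose intensity is 100%.

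**Planned dose intensity without the fluid exception**

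The patient gains fluid from Cycle 2 and the mg dose correctly stays at 0.7W. The rule as written raises the planned dose from Cycle 2. I average the planned intensity over the six cycles, since the SAP does not say how to combine them.

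- 10% gain: mean relative weight = (1 + 5 × 1.10)/6 = 1.0833; 100/1.0833 = 92.3%.
- 15% gain: (1 + 5 × 1.15)/6 = 1.125; 100/1.125 = 88.9%.

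With the fluid exception, both are 100%. This result does not depend on how the averaged weight in the other metric is read.

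**Actual dose level, if measured Day 1 weights are averaged (Q3W, six cycles)**

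Formula: 0.7 / mean relative weight.

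| Weight path | Loss | Gain |
|---|---|---|
| Just under 10% from Cycle 2 | 0.7/0.9167 = 0.764 (+9.1%) | 0.7/1.0833 = 0.646 (-7.7%) |
| Linear drift to 9.9% by Cycle 6 | 0.7/0.9505 = 0.736 (+5.2%) | 0.7/1.0495 = 0.667 (-4.7%) |
| 5% from Cycle 2 | 0.730 (+4.3%) | 0.672 (-4.0%) |
| 15% fluid gain from Cycle 2 | n/a | 0.7/1.125 = 0.622 (-11.1%) |

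The first row is the limit under the 10% rule when the first averaged weight is the dosing weight. If the dosing weight was taken before Cycle 1 Day 1 and all six averaged weights differ from it by 9.9%, the figures are +11.0% and -9.0%.

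**Rituximab.** BSA varies with the square root of weight. A change just under 10% from Cycle 2 gives 1/0.957 = +4.5% (loss) or 1/1.041 = -3.9% (gain), about half the Debio 1562 effect.

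**Actual dose level, if the dosing weights are averaged.** The Q3W patient shows 0.700. This still holds after a 12% change at Cycle 4 with the dosing weight updated.

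**The case against.** The strongest reply on actual dose level is that the SAP never says the averaged weight is the measured one. A reader might infer that it does, but the only explanation of pre-dose weight in the section is the fixed Cycle 1 Day 1 weight. On that reading the Q3W deviation is zero, and an average would still be needed for patients whose dosing weight changes. This stands as far as it goes: the defect is an undefined term, not a proven error. It does not remove the need for wording. The fixed-weight sentence is confined to the planned dose intensity calculation, and averaging a weight that is normally constant would be an odd instruction.

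On planned dose intensity, the missing fluid exception may be shorthand, since it appears earlier in the same section. That is possible, but the metric states its own rule in full and a programmer would follow it as written. Likewise, the listing's reference to the per-protocol dose may point to the protocol's dosing weight, but it does not say so.

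A reader might also infer that the distortion is systematic, with progressing patients appearing over-dosed and oedematous patients under-dosed, or that it could blur the 14% planned difference between regimens (0.8/0.7 = 1.14). The documents do not support this:

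- The weight-loss B-symptom is a loss above 10% (Protocol 8.12), which would normally update the dosing weight.
- Progression is a listed reason for stopping treatment, so six full cycles is a poor model for progressing patients.
- Peripheral oedema is listed without grade or weight effect.
- Both cohorts use the same formula and are summarised by mean, SD and median. Individual gains and losses partly offset.

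Two further points stand. Delivery is also shown through counts of and reasons for interrupted, missed, delayed or decreased doses and through by-subject infusion listings. Dose per kg of current weight is also a legitimate descriptive measure if labelled as such.

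**Conclusion.** The point holds as an inconsistency in SAP 10.4 with limited consequences. The planned dose intensity rule, as written, conflicts with the dosing rule in Protocol 5.7.2. It gives a wrong relative dose intensity for a patient with a fluid gain of 10% or more: 92.3% at 10% and 88.9% at 15%, where 100% is correct, for a gain from Cycle 2 over six cycles. The actual dose level does not define its weight. If measured weights are used, a correctly dosed Q3W patient can show about +9.1% or -7.7% for a change just under 10% from Cycle 2, about 5% with gradual drift, and roughly half the Debio 1562 effect for rituximab. All these figures rest on assumed weight paths.

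Only descriptive exposure outputs are affected. No efficacy, safety or futility analysis in the documents uses them, and nothing shows a bias at cohort level or in the comparison of regimens.

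**What to change.** In SAP 10.4:

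1. Add the fluid-retention exception to the planned dose intensity rule.
2. Define the weight (or BSA) for actual dose level, planned dose intensity and the relative dose intensity listing as the one used to calculate each administered dose. Actual dose level then becomes the sum over administrations of mg given divided by that dosing weight, divided by the number of cycles. A correctly dosed Q3W patient shows exactly 0.700.
3. If an average of measured weights is kept, label it as mg per kg of measured weight and do not compare it with the planned dose.

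This changes no dosing rule. Protocol 5.7.3 gives the rituximab 10% rule without the fluid exception and Appendix J includes it. Those two passages need reconciling, but using the BSA behind each dose means the SAP need not choose between them.

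The cost is a few lines of SAP text and minor programming. There is one small downside: the documents do not say that the dosing weight, or the attribution of a weight change to fluid, is collected in the eCRF. The dosing weight would have to be taken or back-calculated from the infusion and dispensing records (Protocol 5.4 requires doses dispensed to be in the source). Any back-calculation should use the dose prepared and the intended mg/kg level. Using the dose infused would be circular.

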#### **5.7.4. Administration**

##### **5.7.4.1. Debio 1562**

After the pre-infusion prophylaxis regimen is given, Debio 1562 will be administered as follows:

- At 0.7 mg/kg, or other applicable dose as determined by the SRC, as an IV infusion on Day 1 of a 21-day cycle for safety run-in (study Part 1);
- At 0.7 mg/kg, or other applicable dose as determined by the IDMC, as an IV infusion on Day 1 of a 21-day cycle for cohort A (study Part 2);
- At 0.4, 0.2, 0.2 mg/kg, or another applicable dosing regimen as determined by the IDMC, as an IV infusion on Day 1, Day 8 and Day 15, respectively, of a 21-day cycle for cohort B (study Part 2);
- During Part 3 of the study, Debio 1562 will be administered according to the selected dosing regimen(s) studied in Part 2.
- During the COVID-19 pandemic, patients on the Debio 1562 QW regimen can be switched to the Q3W regimen. If a switch to the Q3W regimen is considered by the treating physician to be in the best interest of a given patient to mitigate the COVID-19 risk, the following should be observed:

- the patient must terminate his/her ongoing weekly administration cycle before switching to the Q3W regimen. For instance, if the patient received his/her first weekly administration of 0.4 mg/kg (D1), he/she should continue to receive weekly treatment until the end of that cycle. Only then can the patient start the Q3W dosing regimen (0.7 mg/kg), as an IV infusion on Day 1 of a 21-day cycle – similarly as for cohort A);
- patients who switch should continue to receive the Q3W regimen, following Cohort A treatment schedule for the remainder of the study.

Debio 1562 should be administered first at Day 1 of each cycle, followed by rituximab. An IV tubing administration set with a 0.22 micron in-line filter will be used for infusion.

Initially, Debio 1562 should be administered at a rate of 1 mg/min; after a continuous 30 minutes of infusion, the rate can be increased to 3 mg/min if well tolerated. If well tolerated after a continuous 30 minutes of infusion at 3 mg/min, the rate may be increased to 5 mg/min. Subsequent infusions may be delivered at the tolerated rate. The overall length of infusion will vary depending on dose and patient tolerability; the infusion time will range from approximately 15 to 60 minutes. Following infusion, the IV line should be flushed with normal saline as needed to ensure delivery of the full dose.

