1 INTRODUCTION

This statistical analysis plan (SAP) describes the statistical analyses for the clinical trial Debio 1562-201 entitled "A phase 2 study to evaluate the efficacy and tolerability of Debio 1562 in combination with rituximab in patients with relapsed and/or refractory diffuse large B-cell lymphoma and other forms of non-Hodgkin's lymphoma". This SAP is compliant with protocol amendment 6, dated of 2020-04-24. It will be finalized prior to the database lock for the primary analysis. Production version of the eCRF dated from 2019-03-12 was used.

In this Phase 2 study, the safety and anti-tumor activity of Debio 1562 in combination with rituximab will be investigated for the treatment of subjects with relapsed/refractory (R/R) diffuse large B-cell lymphoma (DLBCL) and other forms of non-Hodgkin's lymphoma (NHL) in study part 1, and in relapsed DLBCL only in study parts 2 and 3.

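### The relative dose intensity listing in SAP 10.4 holds every Cohort B cycle to 0.8 mg/kg, so a fully dosed patient first given the Q3W regimen in Cycles 2-6 is listed at 89.6-97.9% instead of 100%

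*SAP*

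**What the plan says.** SAP 10.4 (Extent of Exposure) defines two versions of relative dose intensity.

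The by-subject listing divides the dose actually received by the planned cumulative dose over the same cycles. The planned cumulative dose "will be calculated as the planned per protocol dose", and a parenthesis then gives the Debio 1562 values: "0.8 mg/kg for Cohort B, 0.7 mg/kg for all other cohorts". This is "multiplied by the number of cycles initiated (up to Cycle 6 or until PD" or the decision to stop treatment, whichever comes first. The value depends on cohort; nothing in the definition refers to a change of regimen.

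The weekly version feeds the summary tables: "The exposure to Debio 1562 and rituximab will be summarized by cohort and overall". Its planned intensity rests on the "Total planned cumulative dose in a cycle". The planned weekly schedule is given "for subjects assigned to the Debio 1562 QW dosing schedule cohort". The section does not say which plan applies after a change of regimen.

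Protocol 5.7.4.1 provides for the change. A patient on the weekly regimen must finish the ongoing weekly cycle: "Only then can the patient start the Q3W dosing regimen (0.7 mg/kg"). After that the patient follows the Cohort A schedule until the end of the study. The SAP Introduction states: "This SAP is compliant with protocol amendment 6, dated of 2020-04-24". Amendment 6 is the one that introduced the switch.

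**The concern.** The SAP's description of the denominator and the number it supplies disagree for a switched patient. The description refers to the protocol's planned dose, which after a switch is that of the Q3W regimen. The number stays at the weekly regimen's total. The SAP handles the switch in disposition (10.1.2) and in the efficacy sensitivity analyses (10.2.3, 10.2.4.1 and 10.2.4.4), but the exposure section has no rule for it.

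A reader takes a relative dose intensity below 100% to mean that drug was missed, withheld or reduced. Here the shortfall would come only from a permitted change of plan made for pandemic logistics. Safety and tolerability form a primary objective, so a dose intensity that mixes the two causes is worth correcting, even in a listing.

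**Working it through.** **Inputs**

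- Weekly regimen: 0.4, 0.2 and 0.2 mg/kg on Days 1, 8 and 15 (SAP 10.4; protocol 5.7.4.1).
- Regimen after a switch: 0.7 mg/kg on Day 1 of each 21-day cycle (protocol 5.7.4.1).
- The switch happens only between cycles and is not reversed (protocol 5.7.4.1). Whole cycles are therefore on one regimen or the other, and at least Cycle 1 is weekly.
- The listing counts initiated cycles up to Cycle 6 (SAP 10.4).
- The efficacy sections of the SAP still class switched patients as Cohort B, so the Cohort B value applies to them.

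**The plan's own figure.** 0.4 + 0.2 + 0.2 = 0.8 mg/kg per cycle. This reproduces exactly and is right for a weekly cycle.

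**Formula.** Let n be the cycles counted (2 to 6) and q the number given Q3W (1 to n - 1). Assume full dosing and a constant dosing weight. Then

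listed value = 100 × [0.8(n - q) + 0.7q] / (0.8n) = 100 × (1 - 0.125 × q/n),

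where 0.125 = (0.8 - 0.7)/0.8. Each Q3W cycle taken alone scores 0.7/0.8 = 87.5%.

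**Six cycles (planned total 6 × 0.8 = 4.8 mg/kg)**

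| Q3W cycles | First Q3W cycle | Received, mg/kg | Listed value |
|---|---|---|---|
| 1 | 6 | 4.7 | 97.9% |
| 2 | 5 | 4.6 | 95.8% |
| 3 | 4 | 4.5 | 93.8% |
| 4 | 3 | 4.4 | 91.7% |
| 5 | 2 | 4.3 | 89.6% |

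**Fewer cycles.** Values for q = 1, 2, … in order:

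- n = 5: 97.5, 95.0, 92.5, 90.0%
- n = 4: 96.9, 93.8, 90.6%
- n = 3: 95.8, 91.7%
- n = 2: 93.8%

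All lie inside the six-cycle range, so 89.6% to 97.9% covers all 15 possible cases.

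**With a cycle-by-cycle denominator.** The planned dose becomes 0.8(n - q) + 0.7q, which equals the dose received, and every case gives 100%.

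**First Q3W dose at Cycle 7 or later.** No Q3W cycle is counted (q = 0), and the listing correctly shows 100%.

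**Why the percentage cannot be read on its own.** A Cohort B patient who misses one 0.2 mg/kg dose under the retreatment rule (protocol 5.9.1) over six cycles scores 4.6/4.8 = 95.8%. A fully dosed patient with two Q3W cycles also scores 95.8%.

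**Weekly measure.** The planned intensity would be 0.8/3 = 0.267 mg/kg/week on the weekly plan or 0.7/3 = 0.233 on the Q3W plan. The SAP does not say which applies after a switch.

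**The case against.** The best defence is that the listing compares what was received with one fixed starting plan per cohort, and that 100% is only one convention. The metric already falls for other patients treated as the protocol directs. A Cohort A cycle at the reduced dose in protocol 5.9.2.2 scores 0.4/0.7 = 57%. A Cohort B cycle with Day 8 skipped under 5.9.1 scores 0.6/0.8 = 75%. Against the assigned weekly plan, a switched patient really did receive 12.5% less per cycle. Switching, every infusion, and dose changes with their reasons are reported elsewhere (SAP 10.1.2 and 10.4), so the case can be reconstructed.

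Part of this stands. The other outputs do allow reconstruction, and the effect is confined to a listing. The analogy does not hold. Reductions and skipped doses are toxicity-driven departures from a plan that stays in force, and the metric exists to show them. The switch replaces the plan. The SAP also does not say that the denominator is the originally assigned plan; it ties it to the protocol. The other outputs explain the percentage but do not correct it.

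Two stronger readings are tempting. A reader might infer that the Cohort B summary of weekly dose intensity is also too low. The documents do not show this: the SAP is silent there, and a schedule-based reading is as available as a cohort-based one. A reader might also infer that the safety tables mishandle patients after a switch. That would argue from absence in a SAP with redacted parts, and it has no bearing on this denominator.

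**Conclusion.** The point holds as a minor error: the rule as written gives a wrong value for any fully dosed patient whose first Q3W dose falls in Cycles 2 to 6. The shortfall is 2.1 to 10.4 percentage points (100 - 97.9 to 100 - 89.6).

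It may affect nobody. Protocol 1.9 counts three patients on the weekly regimen on 14 April 2020, all with permission to switch, and says enrolment was complete. That supports a range of zero to three, provided nobody had already switched before that count. The documents give neither the actual switches nor the cycle at which they occurred, and treatment beyond Cycle 6 was possible (protocol 4.1.1). The percentages also assume a constant dosing weight and no missed or reduced doses.

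No endpoint or analysis population depends on the listing, and SAP 10.2.1 plans no formal comparison between cohorts. The point concerns only the denominator of a descriptive measure. It says nothing about which regimen or dose is appropriate.

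**What to change.** In SAP 10.4, define the planned cumulative dose for the listing as the sum, over the counted cycles, of the dose planned under the regimen the protocol assigns to the patient in that cycle. State that toxicity-driven reductions, delays and skipped doses leave the planned dose unchanged, so that the metric still shows them. Apply the same rule to the weekly planned intensity, where the SAP is silent for switched patients.

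If the sponsor prefers the originally assigned plan as the reference, the SAP should say so, stop describing it as the protocol's planned dose, and footnote switched patients in the listing.

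The cost is one SAP sentence and a little programming for up to three patients. If the weekly measure is currently programmed with the weekly-regimen total throughout, the Cohort B and overall exposure summaries would change slightly. Nothing else in the analysis is touched.
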